# 9.1.1 Reporting of Adverse Events

Report initiation for all AEs and SAEs will begin at the time of the first treatment and continue up until the final study visit (i.e. up to the Follow-up visit). All events will be followed to resolution or until 30 days after the subject completes the study. A final assessment of outcome will be made at that time.

All AEs must be recorded in the subject's medical records and on the eCRFs. AEs will be reported using customary medical terminology along with the following information: the onset and end dates, whether the event is considered to be a SAE (see section 9.2), the impact the event had on study treatment (see section 9.1.2), the CTCAE grade (intensity) of the event (see section 9.1.3), the causality of the event (see section 9.1.4), whether treatment was given as a result of the event (see section 9.1.5), and the outcome of the event (see section 9.1.6).

[figure not shown]
### 9.1.2 Impact of Study Treatment

The impact the event had on the study treatment will be assessed as either: none, study treatment interrupted, study treatment discontinued, or not applicable. The "not applicable" assessment will be used only when the subject is no longer in the treatment phase of the protocol, or if the outcome of the event was "death".

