It is true that allogeneic HCT has the lowest risk of relapse of all therapeutic options for patients with AML and MDS, but transplantation-related mortality can be as high as 20-30%, which can counterbalance the potential advantages. The equilibrium between the increased anti-leukemic efficacy of allogeneic HCT and the risk of non-relapse mortality depends on many factors including the disease risk category, recipient age, donor type, and comorbidities.

In allogeneic HCT, even after histocompatibility matching, risk of recognizing the recipient cells as "foreign" by the donor cells exist. When this recognition happens, an immunological response is initiated by donor T-cells reacting against the recipient antigens. This phenomenon is known as the Graft Versus Host Disease (GVHD). GVHD is one of the major causes of post-transplant morbidity and mortality.

Novel conditioning regimens and immunosuppressive strategies for treatment of GVHD can and have extended the pool of patients eligible for transplantation at the same time as reducing toxic effects in these patients, however GVHD still remains as a significant complication for allogeneic HCT patients.

[figure not shown]
GVHD is categorized into two classes, acute and chronic, based on the timing of the onset after the transplant. Acute GVHD generally occurs within the first 100 days after the transplantation and often involves the skin, liver and the GI tract. Chronic GVHD occurs after 100 days post-transplant and can persist for several years.

There are two commonly used systems for grading of GVHD including the Glucksberg grade (I-IV) and the International Bone Marrow Transplant Registry (IBMTR) grading system (A-D) (Przepiorka D, et al., 1995, Rowlings, PA et al., 1997, Cahn JY et al., 2005). For the purpose of this study Glucksberg grading will be used (see section 7.18).

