### 8.7.6.1 Adverse Events

Adverse events will be coded using Medical Dictionary for Regulatory Activities (MedDRA). TEAEs are defined as events with an onset on or after the first treatment. TEAEs will be summarized by treatment group, System Organ Class, and preferred term. The following TEAE summaries will be provided:

CONFIDENTIAL Page 84 of 108

- Overall TEAEs
- TEAEs by severity grade
- TEAEs by relationship to study treatment.

In addition, separate summaries of SAEs, and AEs resulting in discontinuation of study treatment will be presented.

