# 9.1.8 SC Injection-related Events

SC and IV injections of concentrated protein materials can be associated with injection-related AEs that impact the ability to safely and successfully deliver the drug. Local injection-site reactions may include pain/discomfort, induration, erythema, nodules/cysts, pruritis, ecchymosis, etc. For SC injections, bleeding, absorption of the drug, leakage of drug, and induration at the local injection site can be additional complications. Other AEs that are common to monoclonal antibody-based therapies are chills, headache, backache, malaise, fever, pruritis, rash, nausea, tingling, and hypertension.

SC Injection-site reactions thought to be directly related to the injection are considered to be AEs of special interest, and a separate guideline for the acquisition of data related to this AE of special interest is provided in section 17.1.

# 9.1.9 Stopping Rules for PRO 140

Subjects who develop Grade 1 or Grade 2 adverse events will continue per protocol. If a subject chooses to discontinue study treatment, the site should notify the protocol team leadership, and encourage the subject to complete any remaining study visits until the toxicity resolves.

For subjects who develop Grade 3 or higher adverse events per below, or experience graft failure or relapse the study treatment will be permanently discontinued:

- Grade 3 or higher liver toxicity not attributable to other causes such as infection, GVHD or Sinusoidal Obstruction Syndrome (SOS);
- Grade 3 or higher toxicity which is assessed by the investigator to be definitely, probably or possibly related to the study drug;
- Graft failure or relapse;

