8.4.1 Adverse Events

Adverse events will be coded using Medical Dictionary for Regulatory Activities (MedDRA). TEAEs are defined as events with an onset on or after the first treatment. TEAEs will be summarized by treatment group, System Organ Class, and preferred term. The following TEAE summaries will be provided:

[figure not shown]
- Overall TEAEs
- TEAEs by severity grade

• TEAEs by relationship to study treatment.

In addition, separate summaries of SAEs, and AEs resulting in discontinuation of study treatment will be presented.

8.4.2 Tolerability of repeated subcutaneous administration as assessed by Visual Analogue Scale All data from tolerability assessments of repeated subcutaneous administration of PRO 140 as assessed by study participants (using Visual Analogue Scale, as presented in Figure 8-1: Visual Analog Scale below) and by investigator-evaluation of injection site reactions will be summarized using n, mean, Standard Deviation (SD), minimum and maximum values.

Figure 8-1: Visual Analog Scale

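### Protocol 9.1.2 ties the treatment-impact code to the event's outcome, so the table of adverse events leading to discontinuation may omit fatal events that had stopped study drug

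*Protocol*

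**What the plan says.** - **The field.** Protocol 9.1.2 says the impact of an event on study treatment "will be assessed as either: none, study treatment interrupted, study treatment discontinued, or not applicable". The last code is confined to two situations: the subject is "no longer in the treatment phase of the protocol, or if the outcome of the event was 'death".
- **Where it is recorded.** Protocol 9.1.1 lists what is entered for every adverse event, including "the impact the event had on study treatment (see section 9.1.2"). Events are followed to resolution or until 30 days after the subject completes the study, and then "A final assessment of outcome will be made at that time".
- **What it would feed.** Protocol 8.7.6.1 promises that "separate summaries of SAEs, and AEs resulting in discontinuation of study treatment will be presented". SAP 8.4.1 repeats the summary of "AEs resulting in discontinuation of study treatment". Neither section names a source variable or a derivation.
- **When drug is stopped.** Under Protocol 9.1.9, for subjects who have certain events of Grade 3 or higher, or "experience graft failure or relapse the study treatment will be permanently discontinued".
- **Limit on fatal outcomes.** Protocol 9.1.6 lets only one event per subject carry the outcome of death.

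**The concern.** The field mixes two separate facts: what was done with study drug because of the event, and how the event ended. The first is settled when the dosing decision is made. The second may be settled weeks later. If the later fact overwrites the earlier one, the record of why drug was stopped is lost for exactly those events that went on to kill the subject.

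Safety and tolerability form the secondary objective, and both documents plan descriptive safety summaries only. A reader comparing arms on discontinuations due to adverse events would expect the table to hold every such event. A table that keeps non-fatal stops but may lack fatal ones does not measure what its title says, and nothing in the plan would tell the reader so.

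**Working it through.** The documents give no figure for this point, so the check is a trace through the text followed by a note on scale.

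**Step 1. Can an event stop drug and later become fatal?** Yes. Take a Grade 4 event on Day 20, judged possibly related to study drug. Protocol 9.1.9 requires permanent discontinuation. Protocol 5.2.1 keeps the subject under follow-up where possible. The subject dies of the event on Day 40, and the outcome is entered as death.

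**Step 2. Which impact code results?**
- The question put by 9.1.2, what the event did to study treatment, points to 'study treatment discontinued'.
- The death clause points to 'not applicable'.
- The four codes are alternatives, and no text gives 'discontinued' priority when both fit. On the plain reading the death clause governs.

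**Step 3. Could another event-level item fill the table?** Protocol 9.1.1 lists these items besides the impact code:
- onset and end dates
- seriousness
- CTCAE grade
- causality
- treatment given for the event (9.1.5: none, medication, non-medication therapy, surgery, other)
- outcome

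None records that study drug was stopped. The impact code is the only event-level item described that can. Its use for the table is therefore an inference, but no other event-level source is described.

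**Step 4. Scale.**
- Exposure: at most one event per subject (9.1.6).
- Effect on an arm of 30: 1/30 = 0.033, or 3.3 percentage points per omitted subject. This applies when the fatal event was the only one coded as stopping that subject's drug.
- Count: Protocol 1.2 says "transplantation-related mortality can be as high as 20-30" percent. Applied to 60 subjects, 60 × 0.20 = 12 and 60 × 0.30 = 18 deaths. The share of fatal events that had already stopped drug is not in the documents. Assumed shares give 1.2 to 1.8 events at 10%, 3.0 to 4.5 at 25%, and 6 to 9 at 50%. The spread from about 1 to 9 is driven mainly by the assumed share, so it is not an estimate.

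**The case against.** The case on the other side has four parts.

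1. **The clause limits the code and does not command it.** Section 9.1.2 says when 'not applicable' may be used. It does not say that every fatal event must receive it, or that 'discontinued' is barred when drug was in fact stopped. This stands as a possible reading. It changes the defect from systematic omission to coding that may differ between investigators at up to 20 sites. The sentence needs correcting either way.

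2. **No section says the table is built from this field, and other records exist.** Protocol 5.2 records reasons for stopping treatment or observation. Protocol 8.7.1 and SAP 8.1.1 summarise reasons for discontinuation, and the SAP listing gives the specific reason for each discontinued subject. This stands in part. These records could be reconciled with the event listing, but they are not stated to identify the event, and no reconciliation is planned.

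3. **The fatal events stay visible by arm.** They remain in the overall event summary, in the severity summary as Grade 5 (Protocol Table 9-1), in the SAE summary (Protocol 9.2) and in the listings. The DMC receives adverse events and SAEs (SAP 5.1.2), and mortality above 20% by day +100 triggers its review (Protocol 9.1.10). This stands fully. What those summaries are not stated to show is that study drug was stopped because of the event.

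4. **The table is not a headline result.** The documents define tolerability by pain scores and injection-site reactions, introduce the discontinuation summary as an addition, and attach no test or decision rule to it. This also stands and keeps the point modest.

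**Conclusion.** The defect holds, in a limited form. Section 9.1.2 lets the outcome of an event decide the code for what happened to study drug. The summary of events leading to discontinuation may therefore omit fatal events that had stopped drug, or include them inconsistently. This rests on two assumptions: that sites follow the plain reading (or differ in how they read it), and that the table is derived from the impact code.

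A reader might infer more: that fatal stops are certain to be removed, that a more toxic arm could thereby look safer overall, or that a predictable number of events will be lost. The documents do not support these readings. The wording admits a permissive reading, no source variable is named, and the deaths appear by arm in other planned summaries. The mortality figure is an upper value for transplant-related death with no time horizon, and it says nothing about how many subjects had drug stopped first. The supportable statement of size is at most one event per subject and 3.3 percentage points per omitted subject in an arm of 30.

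**What to change.** **Protocol 9.1.2 and the eCRF completion guide.** Delete the clause that ties 'not applicable' to a fatal outcome. Say that the action taken with study drug because of the event is recorded as it stood at the time and is not changed by the later outcome. Keep 'not applicable' for events that begin after dosing has already ended, and for events where death came before any dosing decision. The first of these needs careful wording. An event that starts between two doses and causes the next to be withheld for good has its onset after the last dose given, yet it must still be coded as a discontinuation.

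**SAP 8.4.1.** Say that the discontinuation summary includes every event that led to discontinuation of study treatment, whatever its outcome.

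**Cost.** One sentence in the protocol and eCRF guide and one in the SAP. No new data are needed, and no dosing or stopping rule changes.

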## 9.1.3 CTCAE Grade (Severity) Assessment

The investigator will carefully evaluate the comments of each subject and the response to treatment in order to judge the true nature and severity of the AE. To assess severity, the

CONFIDENTIAL Page 86 of 108

investigator will use the guidelines outlined in CTCAE v4.03. The general guidelines for assessing the AE grade appear below. Full guidelines may be obtained at http://evs.nci.nih.gov/ftp1/CTCAE.

**Table 9-1: CTCAE v4.03 General Guidelines** 

Grade	Description
Grade 1	Mild; asymptomatic or mild symptoms; clinical or diagnostic observations only; intervention not indicated.
Grade 2	Moderate; minimal, local, or noninvasive intervention indicated; limiting age- appropriate instrumental activities of daily living (ADL)*.
Grade 3	Severe or medically significant but not immediately life-threatening; hospitalization or prolongation of hospitalization indicated; disabling; limiting self care ADL†.
Grade 4	Life-threatening consequences; urgent intervention indicated.
Grade 5	Death related to AE.

\*Instrumental ADL refer to preparing meals, shopping for groceries or clothes, using the telephone, managing money, etc.

# 9.1.4 Causality Assessment

[figure not shown]
Adverse events will be assigned a relationship (causality) to the study treatment. The Principal Investigator (PI) must review each AE and make the determination of relationship of the event to the study treatment. Relationship of AEs to study treatment will be classified as follows:

- 1. **Definitely related**: This category applies to those AEs that the Investigator feels are incontrovertibly related to the study treatment. An AE may be assigned an attribution of definitely related if or when it meets all of the following criteria: (1) it follows a reasonable temporal sequence from administration of the study treatment; (2) it could not be reasonably explained by the known characteristics of the subject's clinical state, environmental or toxic factors, or other modes of therapy administered to the subject; (3) it follows a known response pattern to treatment with the study treatment.
- 2. **Probably related:** This category applies to those AEs which, after careful medical consideration at the time they are evaluated, are felt with a high degree of certainty to be related to the study treatment. An AE may be considered probable if or when (must have three): (1) it follows a reasonable temporal sequence from administration of the study treatment. (2) It could not readily have been produced by subject's clinical state, environmental or toxic factors, or other therapies administered to the subject. (3) Disappears or is decreased upon discontinuation of the study treatment. (4) It follows a

CONFIDENTIAL Page 87 of 108

†Self care ADL refer to bathing, dressing and undressing, feeding self, using the toilet, taking medications, and not bedridden.

Common Terminology Criteria for Adverse Events (CTCAE), v4.03: June 14, 2010

known response pattern to treatment with the study treatment.

- 3. **Possibly related**: This category applies to those AEs which, after careful medical consideration at the time they are evaluated, are judged unlikely but cannot be ruled out with certainty to the study treatment. An AE may be considered possible if or when (must have two): (1) it follows a reasonable temporal sequence from administration of the study treatment. (2) It could not readily have been produced by subject's clinical state, environmental or toxic factors, or other therapies administered to the subject. (3) Disappears or is decreased upon discontinuation of the study treatment. (4) It follows a known response pattern to treatment with the study treatment.
- 4. **Remotely related**: In general this category can be considered applicable to those AEs which, after careful medical consideration at the time they are evaluated, are judged likely to be unrelated to the study treatment. An AE may be considered unlikely if or when (must have two): (1) it does not follow a reasonable temporal sequence from administration of the study treatment. (2) It could not readily have been produced by subject's clinical state, environmental or toxic factors, or other therapies administered to the subject. (3) Disappears or is decreased upon discontinuation of the study treatment. (4) It does not follow a known response pattern to treatment with the study treatment.
- 5. **Unrelated**: This category applies to those AEs which, after careful consideration at the time they are evaluated, are clearly and incontrovertibly due to extraneous causes (disease, environment, etc.) and determined with certainty to have no relationship to the study treatment.

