# 9.1.10 Study Stopping Rules

Upon occurrence of any of the following events, data will be reviewed by the Data Monitoring Committee (DMC):

- 1. Occurrence of a Grade 4 toxicity or two (2) occurrences of Grade 3 toxicities that are assessed to be definitely, probably or possibly study drug-related by the treating investigator;
- 2. Occurrence of more than 20 percent mortality by day +100;
- 3. Occurrence of more than 5 percent graft failures by day +100;
- 4. Occurrence of 5 or more of the first 10 subjects experiencing acute Grade II-IV GVHD.

CONFIDENTIAL Page 89 of 108

Version 3.0 Date: 17 Jun 2016

The DMC will make a recommendation to the study investigators, who, in consultation with the sponsor will decide whether to stop enrollment in the study.

[figure not shown]

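### Two of the four Remotely related criteria in Protocol 9.1.4 point towards a drug effect, so one event can meet both Possibly and Remotely related, and no rule says which applies

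*Protocol*

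**What the plan says.** Protocol 9.1.4 defines five levels of relationship. Each opens with an overall investigator judgement, and all but *Unrelated* then give a checklist.

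- *Possibly related*: "An AE may be considered possible if or when (must have two" of four features. These are fitting timing, no ready alternative explanation, improvement when study drug is stopped, and a known response pattern.
- *Remotely related*: "An AE may be considered unlikely if or when (must have two" of four. The first is "1) it does not follow a reasonable temporal sequence from administration of the study treatment". The second is "2) It could not readily have been produced by subject's clinical state, environmental or toxic factors, or other therapies administered to the subject". The third and fourth are "3) Disappears or is decreased upon discontinuation of the study treatment. (4) It does not follow a known response pattern to treatment".
- *Probably related* needs three of the *Possibly* features. *Definitely related* needs timing, no alternative explanation and known pattern together. *Unrelated* requires certainty that there is no relationship.

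Two safety rules use the scale. Section 9.1.9 permanently stops study treatment for "Grade 3 or higher toxicity which is assessed by the investigator to be definitely, probably or possibly related to the study drug". The first DMC trigger in 9.1.10 is one Grade 4 or two Grade 3 toxicities "that are assessed to be definitely, probably or possibly study drug-related by the treating investigator". *Remotely* is in neither list. SAP 8.4.1 plans a summary of "TEAEs by relationship to study treatment" and does not redefine the levels.

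**The concern.** *Remotely related* is meant for events the investigator thinks are probably not due to the drug. Having no other explanation, and improving when the drug is withdrawn, are reasons to think the opposite. The list looks like an incomplete negation of the *Possibly* list: (1) and (4) were reversed, while (2) and (3) were carried over as they stood.

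The boundary between *Possibly* and *Remotely* decides whether a Grade 3 or higher toxicity counts under the causality-based criterion in 9.1.9 and under the first trigger in 9.1.10. If the same facts satisfy both definitions, two investigators can code the same event on opposite sides of that boundary, each within the text. The relationship table in the report inherits the same ambiguity.

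**Working it through.** The plan gives no figure to reproduce, so the check is logical. Score four features as 1 (present) or 0 (absent): T, timing fits; N, not readily explained otherwise; D, improves on stopping; K, known pattern. This gives 2^4 = 16 profiles.

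**Definitions from 9.1.4**
- *Possibly*: T + N + D + K ≥ 2.
- *Probably*: T + N + D + K ≥ 3.
- *Definitely*: T = N = K = 1.
- *Remotely* as printed: (1−T) + N + D + (1−K) ≥ 2, which is the same as N + D ≥ T + K.

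**Counts as printed**
- *Possibly*: 6 + 4 + 1 = 11 profiles (exactly two, three or four features).
- *Remotely*: with N+D = 0, T+K must be 0, 1 profile. With N+D = 1, T+K ≤ 1, 2 × 3 = 6. With N+D = 2, T+K can be anything, 4. Total 1 + 6 + 4 = 11.
- *Remotely* but not *Possibly*: no features, N only, D only, so 3 profiles.
- Both: 11 − 3 = 8, namely TN, TD, ND, NK, DK, TND, NDK and TNDK.
- Neither: 16 − (11 + 11 − 8) = 2, namely T only and K only.

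The direction is also perverse. An event with fitting timing alone does not meet *Remotely*. If it also improves on stopping (TD), it does.

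**When study drug has not been stopped.** With D = 0 there are 8 profiles. Four meet *Possibly* (TN, TK, NK, TNK) and four meet *Remotely* (none, N, TN, NK). Two meet both (TN, NK), and T only and K only still meet neither.

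**Effect of negating (2) and (3), keeping two of four.** *Remotely* becomes T + N + D + K ≤ 2.
- If D can be judged, no profile meets both *Remotely* and *Probably*, and none meets neither *Possibly* nor *Remotely*. The 6 profiles with exactly two features still meet both of those categories, so a precedence rule is needed.
- If drug was not stopped, the result depends on how the negated criterion (3) is scored. Scored as not met, *Possibly* needs T+N+K ≥ 2 and *Remotely* needs T+N+K ≤ 1: no overlap and no gap. Scored as met, *Remotely* needs T+N+K ≤ 2, and 3 of 8 profiles meet both. The protocol must therefore say which applies.
- Requiring three of four negated criteria removes the overlap when D can be judged. When drug was not stopped and (3) is scored as not met, T only, N only and K only then meet neither: 3 of 8, against 2 of 8 as printed.

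**The case against.** The checklist is not the whole definition. Each level begins with an overall judgement, and the criteria are permissive. A reader who only enumerates profiles might infer that the flaw reaches further up the scale, since 3 of the 5 *Probably* profiles and 1 of the 2 *Definitely* profiles also satisfy the printed *Remotely* checklist. The documents do not support that. *Probably* requires a high degree of certainty that the drug is responsible, *Definitely* requires that this be beyond dispute, and neither fits with a judgement that the event is probably unrelated. The overlap with *Possibly* survives, because that level covers events thought unlikely to be drug-related but impossible to exclude, which is nearly the judgement that opens *Remotely*.

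A reader might also infer that a miscoded event triggers nothing. That is too strong:
- In 9.1.9, Grade 3 or higher liver toxicity not attributable to other causes, graft failure and relapse stop treatment without using this scale. Protocol 5.2 lets the investigator discontinue a subject at any time.
- In 9.1.10, triggers 2 to 4 (mortality, graft failure, GVHD) do not use causality. One Grade 3 event never fires trigger 1; miscoding removes it from the count of two. The sentence leaves open whether the causality condition covers Grade 4 at all.
- Under SAP section 5, the DMC receives AEs and SAEs at the interim analysis with no stated causality filter. Protocol section 12 lets it meet when it sees fit, and 9.2.1 requires every SAE in the reporting period to be reported.
- In the positive-withdrawal case the drug has by definition already been interrupted or stopped. What escapes is the permanent stop.

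Finally, 8 of 11 counts unweighted profiles. It is not a rate of miscoded events, and nothing in the documents says how often any profile occurs in this population.

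**Conclusion.** The *Remotely related* definition is wrong as written. Two of its four criteria support the conclusion opposite to the category's meaning. On the checklists alone, 8 of the 11 *Possibly* profiles also meet *Remotely* (2 of the 4 when drug has not been stopped), two profiles meet neither, and no precedence rule exists. These counts assume that each feature can be scored yes or no and set the opening judgement aside.

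The consequence is real but bounded. A Grade 3 or higher event could be coded *Remotely* within the text and so drop out of the causality-based criterion in 9.1.9 and the first trigger in 9.1.10, subject to the Grade 4 ambiguity. The effect on the SAP is confined to a descriptive table, since SAP 8.4 plans no inference on safety. The primary endpoint, sample size and efficacy analyses are untouched. This should be fixed, but it does not threaten the trial's main result.

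**What to change.** In Protocol 9.1.4, item 4:
1. Negate criteria (2) and (3), as (1) and (4) already are.
2. State that an event meeting more than one category is coded to the highest category met. This settles the six profiles that would still meet both *Possibly* and *Remotely*.
3. State how criterion (3) is scored when study drug was not stopped.
4. State where an event that meets no checklist is placed, so that every event has exactly one category. This is still needed where several criteria cannot be judged.

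Raising the threshold to three of four is not recommended, because it leaves more profiles unplaced when dosing continues.

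The sponsor must then reconcile the corrected definitions with 9.1.9 and 9.1.10, including whether the causality condition in the first trigger applies to Grade 4, and use them for the relationship table in SAP 8.4.1. This point takes no position on what those stopping rules should be.

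The cost is a short change of protocol wording and a memo to sites. A few more events may be coded *Possibly related*.
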